3.6.1 Withdrawal of Consent

Subjects who request to discontinue study drug will remain in the study and must continue to be followed for protocol specified follow-up procedures. The only exception to this is when a subject specifically withdraws consent for any further contact with him/her or persons previously authorized by subject to provide this information. Subjects should notify the investigator of the decision to withdraw consent from future follow-up **in writing**, whenever possible. The withdrawal of consent should be explained in detail in the medical records by the investigator, as to whether the withdrawal is from further treatment with study drug only or also from study procedures and/or post treatment study follow-up, and entered on the appropriate CRF page. In the event that vital status (whether the subject is alive or dead) is being measured, publicly available information should be used to determine vital status only as appropriately directed in accordance with local law.

3.6.2 Lost to Follow-Up

All reasonable efforts must be made to locate subjects to determine and report their ongoing status. This includes follow-up with persons authorized by the subject as noted above. Lost to follow-up is defined by the inability to reach the subject after a minimum of three documented phone calls, faxes, or emails as well as lack of response by subject to one registered mail letter. All attempts should be documented in the subject's medical records. If it is determined that the subject has died, the site will use permissible local methods to obtain the date and cause of death.

If investigator's use of third-party representative to assist in the follow-up portion of the study has been included in the subject's informed consent, then the investigator may use a Sponsor-retained third-party representative to assist site staff with obtaining subject's contact information or other public vital status data necessary to complete the follow-up portion of the study. The site staff and representative will consult publicly available sources, such as public health registries and databases, in order to obtain updated contact information. If after all attempts, the subject remains lost to follow-up, then the last known alive date as determined by the investigator should be reported and documented in the subject's medical records.

4 STUDY DRUG

Study drug includes both Investigational [Medicinal] Product (IP/IMP) and Non-investigational [Medicinal] Product (Non-IP/Non-IMP). All study drugs are listed in [Table 4-1](#).

| Table 4-1: Study Drugs for BMS-936558 - Treatment Phase | | | | | |
|--|-------------------|-------------------|------------------------------|--|---|
| Product Description / Class and Dosage Form | Potency | IP/Non-IMP | Blinded or Open Label | Packaging/ Appearance | Storage Conditions (per label) |
| Nivolumab Solution for Injection ^a | 100 mg (10 mg/mL) | IP | Open Label | 10 mL per vial/ 5 or 10 vials per box Vials contain clear to opalescent colorless to pale yellow liquid. May contain particles | 2° to 8°C. Protect from light and freezing |
| Topotecan hydrochloride concentrate for solution for infusion ^b | 4 mg (1 mg/mL) | IP | Open Label | 4 mg per vial/ 1 or 5 vials per box Vials contain clear yellow to yellow/green solution | Store at 2° to 8°C. Protect from freezing and light. Store in outer carton. |
| Topotecan hydrochloride powder for infusion ^b | TBC | IP | Open Label | TBC | Store at 15° to 25°C. Protect from freezing and light. Store in outer carton. |
| Topotecan capsule ^b | 0.25 mg/ 1 mg | IP | Open Label | TBC | Store at 2° to 8°C. Protect from freezing and light. Store in outer carton. |
| Amrubicin hydrochloride powder for solution for injection ^b | 50 mg | IP | Open Label | 50 mg per vial/ 1 vial per box Vials contain yellow-red powder or mass | Store at 15° to 25°C. |

^a Labeled as either “BMS-936558-01” or “Nivolumab”

^b For sites/countries in which the marketed product of topotecan and/or amrubicin, will be procured locally, the potency, packaging configuration and storage conditions may differ based on the locally available product.

4.1 Investigational Product

An investigational product, also known as investigational medicinal product in some regions, is defined as a pharmaceutical form of an active substance or placebo being tested or used as a reference in a clinical study, including products already with a marketing authorization but used or assembled (formulated or packaged) differently than the authorized form, or used for an unauthorized indication, or when used to gain further information about the authorized form.

The investigational product should be stored in a secure area according to local regulations. It is the responsibility of the investigator to ensure that investigational product is only dispensed to study subjects. The investigational product must be dispensed only from official study sites by authorized personnel according to local regulations.

In this protocol, investigational product(s) are:

- Nivolumab
- Topotecan
- Amrubicin

4.1.1 Nivolumab

Nivolumab 240 mg (flat dose) on Day 1 of a 14-day cycle as an IV infusion over 30 minutes. Please refer to the current version of the Investigator Brochure and/or pharmacy reference sheets for complete storage, handling, preparation, and administration information for nivolumab.

4.1.2 Topotecan

Topotecan: 1.5 mg/m² administered as 30-minute IV infusion or 2.3 mg/m² administered as an oral capsule (round dose to nearest 0.25 mg) once daily on Days 1 to 5 of a 21-day cycle. Please refer to the current version of the Summary of Product Characteristics (SmPC), US Package Insert (USPI), or other country-specific labeling and/or pharmacy reference sheet for complete storage, handling, preparation, and administration information for topotecan.

4.1.3 Amrubicin

Amrubicin (upon investigator's choice, where locally approved for 2nd line SCLC treatment): 40 mg/m² administered as 5-minute IV infusion once daily on Days 1 to 3 of a 21-day cycle. Please refer to the current version of the country-specific labeling and/or pharmacy reference sheet for complete storage, handling, preparation, and administration information for amrubicin.

4.2 Non-investigational Product

Other medications used as support or escape medication for preventative, diagnostic, or therapeutic reasons, as components of the standard of care for a given diagnosis, may be considered as non-investigational products.

In this protocol, non-investigational product(s) is/are: any pre-medications associated with the comparator arms and medications used to treat chemotherapy infusion-related reactions. Also, any medications used to treat nivolumab infusion-related reactions (eg. steroids). These non-

investigational products should be sourced by the investigator sites if available and permitted by local regulations.

4.3 Storage and Dispensing

The product storage manager should ensure that the study drug is stored in accordance with the environmental conditions (temperature, light, and humidity) as determined by BMS. If concerns regarding the quality or appearance of the study drug arise, the study drug should not be dispensed and contact BMS immediately.

Study drug not supplied by BMS will be stored in accordance with the package insert.

Investigational product documentation (whether supplied by BMS or not) must be maintained that includes all processes required to ensure drug is accurately administered. This includes documentation of drug storage, administration and, as applicable, storage temperatures, reconstitution, and use of required processes (eg, required diluents, administration sets).

4.4 Method of Assigning Subject Identification

4.4.1 Screening

After informed consent has been obtained, the subject must be enrolled into the study by calling an interactive IVRS to obtain the subject number. The following information is required for subject registration:

- Date of birth
- Date of informed consent
- Gender.

4.4.2 Randomization

Once a subject has been determined to meet eligibility criteria, site personnel will make another call to the IVRS. The following information is required for subject randomization:

- Subject number
- Confirmation that all randomization inclusion/exclusion are met
- Confirmation that FFPE tumor tissue block or unstained slides were received by the central laboratory
- Response to first-line platinum-based treatment: platinum sensitive vs platinum resistant
- Brain metastases at baseline: yes vs no.

If the above are met, the IVRS will randomly assign subjects to treatment Arm A or Arm B in a 1:1 ratio using a stratified permuted block randomization method with respect to the following stratification factors:

- Response to first-line platinum based treatment: platinum sensitive vs platinum resistant
- Brain metastases at baseline: yes vs no.

The first dose of study drug is to be administered within 3 business days following randomization.

Randomization will be performed based on a randomization schedule generated and maintained by the Randomization Group within Bristol-Myers Squibb.

The procedures for using the IVRS will be detailed in a separate document.

4.5 Selection and Timing of Dose for Each Subject

4.5.1 Dosing Schedule

The dosing schedule is detailed below Table 4.5.1-1.

| Table 4.5.1-1: Dosing Schedule | | | | | | |
|---|------------------------|---------------|--------------------|------------------------|--------------------|---------------|
| | Week 1 | Week 2 | Week 3 | Week 4 | Week 5 | Week 6 |
| Arm A | | | | | | |
| Nivolumab 240 mg ^a q 2 weeks | Day 1 Nivolumab | | Day 1 Nivolumab | | Day 1 Nivolumab | |
| Arm B | | | | | | |
| Topotecan ^a IV 1.5 mg/m ² or capsule 2.3 mg/m ² or | Day 1 - 5 Topotecan | | | Day 1 - 5 Topotecan | | |
| Amrubicin ^a 40 mg/m ² | Day 1 - 3 Amrubicin | | | Day 1 - 3 Amrubicin | | |

^a Treatment continues until disease progression (or until discontinuation of study drug in subjects receiving nivolumab), discontinuation due to toxicity, withdrawal of consent, or the study ends.

All subjects will be monitored continuously for AEs while on study treatment. Treatment modifications (eg, dose delay, reduction, or discontinuation) will be based on specific laboratory and AE criteria, as described in Sections 4.5.2 and 4.5.3.

4.5.1.1 Nivolumab

For subjects randomized to Arm A, nivolumab will be administered as a flat dose of 240 mg on Day 1 of a 14-day cycle as an IV infusion over 30 minutes. The rationale for this dosage schedule is provided in Section 1.1.6.

Refer to the Pharmacy Information sheets for more detail. There are no pre-medications recommended on the first cycle. If an acute infusion reaction is noted, subjects should be managed according to Section 4.5.5.

Dosing Window: Subjects may be dosed no less than 12 days between doses and no more than 3 days from scheduled dose. If an infusion cannot be administered at a scheduled visit, it should be administered as soon as possible. Subsequent dosing visits will follow every 2 weeks after the delayed dose.

A dose given more than 3 days after the intended dose date will be considered a delay. A maximum delay of 6 weeks between doses is allowed. Longer delays may be allowed following discussion with the Medical Monitor, as described in [Section 4.5.3.1](#).

Management Algorithms for Immuno-Oncology Agents

Immuno-oncology agents are associated with AEs that can differ in severity and duration than AEs caused by other therapeutic classes. Nivolumab is considered immuno-oncology agent in this protocol. Early recognition and management of AEs associated with immuno-oncology agents may mitigate severe toxicity. Management algorithms have been developed to assist investigators in assessing and managing the following groups of AEs:

- Gastrointestinal
- Renal
- Pulmonary
- Hepatic
- Endocrinopathies
- Skin
- Neurological.

The algorithms are found in the Investigator Brochure and [Appendix 1](#) of this protocol.

Changes in tumor measurements and tumor responses will be assessed by the investigator using the RECIST 1.1 criteria. Please refer to [Appendix 2](#) for the specifics of the RECIST 1.1 criteria to be utilized in this study.

4.5.1.2 Topotecan

Subjects randomized to Arm B will receive treatment with topotecan 1.5 mg/m² IV infusion or 2.3 mg/m² oral capsule (round dose to nearest 0.25 mg) on Days 1 through 5 every 3 weeks (21 days). Refer to the local product label for more details.

Dosing Window: Subjects may be dosed no less than 14 days from the last dose of the previous cycle and no more than 3 days from scheduled dose. If an infusion cannot be administered at a scheduled visit, it should be administered as soon as possible. Subsequent dosing visits will follow every 3 weeks after the delayed dose.

A dose given more than 3 days after the intended dose date will be considered a delay. A maximum delay of 6 weeks between doses is allowed. Longer delays may be allowed following discussion with the Medical Monitor, as described in [Section 4.5.3.1](#).

4.5.1.3 Amrubicin

Subjects randomized to Arm B will receive treatment with amrubicin 40 mg/m² on Days 1 through 3 every 3 weeks (21 days). Refer to the local product label for more detail.

Dosing Window: Subjects may be dosed no less than 16 days from the last dose of the previous cycle and no more than 3 days from scheduled dose. If an infusion cannot be administered at a scheduled visit, it should be administered as soon as possible. Subsequent dosing visits will follow every 3 weeks after the delayed dose.

A dose given more than 3 days after the intended dose date will be considered a delay. A maximum delay of 6 weeks between doses is allowed. Longer delays may be allowed following discussion with the Medical Monitor, as described in [Section 4.5.3.1](#).

4.5.2 Dose Modifications and Dose Delays

This section includes information on dose modifications, dose delays, and provides guidelines for resuming treatment after a dose delay. Tumor assessments for all subjects should continue as per protocol even if dosing is delayed.

4.5.2.1 Nivolumab

No dose modifications of nivolumab are allowed for the management of toxicities experienced by individual subjects.

Dose delay criteria apply for all drug-related AEs. Treatment delays up to 6 weeks (42 days) from the last dose are allowable.

Nivolumab administration should be delayed for the following:

- Grade 2 non-skin, drug-related adverse event, with the exception of fatigue
- Grade 2 drug-related creatinine, AST, ALT and/or Total Bilirubin abnormalities
- Grade 3 skin, drug-related adverse event
- Grade 3 drug-related laboratory abnormality, with the following exceptions:
 - Grade 3 lymphopenia or asymptomatic amylase or lipase does not require dose delay
 - Grade ≥ 3 AST, ALT, Total Bilirubin will require dose discontinuation (see [Section 4.5.3.1](#))
- Any adverse event, laboratory abnormality, or intercurrent illness which, in the judgment of the investigator, warrants delaying the dose of study medication.

Subjects who require delay of nivolumab should be re-evaluated weekly or more frequently if clinically indicated and resume nivolumab dosing when re-treatment criteria are met

Criteria to Resume Treatment

Subjects may resume treatment with nivolumab when the drug-related AE(s) resolve to Grade ≤ 1 or baseline value, with the following exceptions:

- Subjects may resume treatment in the presence of Grade 2 fatigue
- Subjects who have not experienced a Grade 3 drug-related skin AE may resume treatment in the presence of Grade 2 skin toxicity
- For subjects with Grade 2 AST, ALT and/or Total Bilirubin Abnormalities, dosing may resume when laboratory values return to baseline and management with corticosteroids, if needed, is complete.
- Subjects with combined Grade 2 AST/ALT AND total bilirubin values meeting discontinuation parameters (Section 4.5.3.1) should have treatment permanently discontinued
- Drug-related pulmonary toxicity, diarrhea or colitis must have resolved to baseline before treatment is resumed. Subjects with persistent Grade 1 pneumonitis after completion of a steroid taper over at least 1 month may be eligible for retreatment if discussed with and approved by BMS Medical Monitor.
- Subjects with drug-related endocrinopathies adequately controlled with only physiologic hormone replacement may resume treatment after consultation with the BMS Medical Monitor. Adrenal insufficiency requires discontinuation regardless of control with hormone replacement

If the criteria to resume treatment are met, the subject should restart treatment at the next scheduled timepoint per protocol.

If treatment is delayed > 6 weeks (42 days) from the last dose, the subject must be permanently discontinued from study therapy, except as specified in Section 4.5.3.1.

4.5.2.2 Topotecan

Dose modifications and dose delays for the management of toxicities experienced by individual subjects in Arm B who are receiving topotecan are provided in Table 4.5.2.2-1. In addition, treatment may be delayed for any AE, laboratory abnormality, or intercurrent illness which, in the judgment of the investigator, warrants delaying the dose of study medication.

| Table 4.5.2.2-1: Topotecan Dose Modifications and Delays | |
|--|---|
| Adverse Event | Dose Modification |
| ANC < 1000/mm ³ and/or Platelets < 100,000/mm ³ at Day 1 | Delay treatment until: ANC ≥ 1000/mm ³ Platelets > 100,000/mm ³ |
| Toxicity Grade < 2 during previous cycle | Optional, based on local treatment guidelines: Increase IV topotecan dosage to a maximum of 2 mg/m ² per day in increments of 0.25 mg/m ² per day. Increase oral topotecan dosage to a maximum of 3.1 mg/m ² in increments of 0.4 mg/m ² per day. |
| Grade 4 neutropenia with fever or infection, or of duration ≥ 7 days Grade 3 neutropenia during the preceding cycle persisting after Day 21 Grade 4 thrombocytopenia | Reduce IV topotecan dosage by 0.25 mg/m ² per day. Reduce oral topotecan dosage by 0.4 mg/m ² per day. |
| Grade 3/4 Nonhematologic toxicity, excluding Grade 3 nausea | Reduce IV topotecan dosage by 0.25 mg/m ² per day or discontinue treatment. Reduce oral topotecan dosage by 0.4 mg/m ² per day or discontinue treatment. |
| Treatment delay > 6 weeks | Discontinue treatment |

ANC = absolute neutrophil count

Note: The minimum permissible daily IV topotecan dosage is 1 mg/m²; the minimum daily oral topotecan dosage is 1.5 mg/m².

Criteria to Resume Treatment

Subjects may resume treatment with topotecan when the drug-related AE(s) resolve to Grade ≤ 1 or baseline value, with the following exceptions:

- Treatment can be resumed when ANC ≥ 1000/mm³ and platelets > 100,000/mm³
- Subjects may resume treatment in the presence of Grade 2 fatigue
- Subjects who have not experienced a Grade 3 drug-related skin AE may resume treatment in the presence of Grade 2 skin toxicity
- Drug-related pulmonary toxicity must have resolved to baseline before treatment is resumed.

If the criteria to resume treatment are met, the subject should restart treatment at the next scheduled timepoint per protocol.

If treatment is delayed > 6 weeks (42 days) from the last dose, the subject must be permanently discontinued from study therapy, except as specified in [Section 4.5.3.2](#).

When resuming topotecan treatment, please follow the dose reduction recommendations noted in [Table 4.5.2.2-1](#).

4.5.2.3 Amrubicin

Dose modifications and dose delays for the management of toxicities experienced by individual subjects in Arm B who are receiving amrubicin are provided in [Table 4.5.2.3-1](#). In addition, treatment may be delayed for any AE, laboratory abnormality, or intercurrent illness which, in the judgment of the investigator, warrants delaying the dose of study medication.

| Table 4.5.2.3-1: Amrubicin Dose Modifications | |
|--|---|
| Amrubicin: Dose Modifications and Delays | |
| Adverse Event | Dose Modification |
| ANC < 1000/mm ³ and/or Platelets < 100,000/mm ³ at Day 1 | Delay treatment until: ANC ≥ 1000/mm ³ Platelets ≥ 100,000/mm ³ |
| Grade 4 neutropenia with fever or infection, or of duration ≥ 7 days Grade 3 neutropenia during the preceding cycle persisting after Day 21 Grade 4 thrombocytopenia | Reduce amrubicin dosage by 5 mg/m ² per day |
| Grade 3/4 Nonhematologic toxicity, excluding Grade 3 nausea | Reduce amrubicin dosage by 5 mg/m ² per day |
| Treatment delay > 6 weeks | Discontinue treatment |

ANC = absolute neutrophil count

Criteria to Resume Treatment

Subjects may resume treatment with amrubicin when the drug-related AE(s) resolve to Grade ≤ 1 or baseline value, with the following exceptions:

- Treatment can be resumed when ANC ≥ 1000/mm³, and platelets ≥ 100,000/mm³
- Subjects may resume treatment in the presence of Grade 2 fatigue
- Subjects who have not experienced a Grade 3 drug-related skin AE may resume treatment in the presence of Grade 2 skin toxicity
- Drug-related pulmonary toxicity must have resolved to baseline before treatment is resumed.

If the criteria to resume treatment are met, the subject should restart treatment at the next scheduled timepoint per protocol.

If treatment is delayed > 6 weeks (42 days) from the last dose, the subject must be permanently discontinued from study therapy, except as specified in [Section 4.5.3.3](#).

When resuming amrubicin treatment, please follow the dose reduction recommendations noted in Table 4.5.2.3-1.

4.5.3 Discontinuation Criteria

4.5.3.1 Nivolumab

Treatment with nivolumab should be permanently discontinued for the following:

- Grade 2 drug-related uveitis, eye pain or blurred vision that does not respond to topical therapy and does not improve to Grade 1 severity within the re-treatment period OR requires systemic treatment
- Grade 3 non-skin, drug-related adverse event lasting > 7 days or recurs, with the following exceptions for laboratory abnormalities, drug related uveitis, pneumonitis, bronchospasm, neurologic toxicity, hypersensitivity reactions, infusion reactions and endocrinopathies:
 - Grade 3 drug-related uveitis, pneumonitis, bronchospasm, neurologic toxicity, myocarditis, hypersensitivity reaction, or infusion reaction of any duration require discontinuation
 - Grade 3 drug-related endocrinopathies adequately controlled with only physiologic hormone replacement do not require discontinuation; Adrenal insufficiency requires discontinuation regardless of control with hormone replacement.
 - Grade 3 drug-related laboratory abnormalities do not require treatment discontinuation except:
 - ◆ Grade 3 drug-related thrombocytopenia > 7 days or associated with bleeding requires discontinuation
 - ◆ Grade ≥ 3 drug-related AST, ALT or Total Bilirubin requires discontinuation*
 - ◆ Concurrent AST or ALT > 3 x ULN and total bilirubin > 2x ULN
- * In most cases of Grade 3 AST or ALT elevation, study drug(s) will be permanently discontinued. If the investigator determines a possible favorable benefit/risk ratio that warrants continuation of study drug(s), a discussion between the investigator and the BMS Medical Monitor/designee must occur
- Any Grade 4 drug-related adverse event or laboratory abnormality (including but not limited to creatinine, AST, ALT, or Total Bilirubin) except for the following events which do not require discontinuation:
 - Grade 4 neutropenia ≤ 7 days
 - Grade 4 lymphopenia or leukopenia or asymptomatic amylase or lipase
 - Isolated Grade 4 electrolyte imbalances/abnormalities that are not associated with clinical sequelae and are corrected with supplementation/appropriate management within 72 hours of their onset
 - Grade 4 drug-related endocrinopathy adverse events, such as hyper- or hypothyroidism, or glucose intolerance, which resolve or are adequately controlled with physiologic hormone replacement (corticosteroids, thyroid hormones) or glucose-controlling agents,

respectively, may not require discontinuation after discussion with and approval from the BMS Medical Monitor.

- Any event that leads to delay in dosing lasting > 6 weeks from the previous dose requires discontinuation, with the following exceptions:
 - Dosing delays to allow for prolonged steroid tapers to manage drug-related adverse events are allowed.
 - Dosing delays lasting > 6 weeks from the previous dose that occur for non-drug-related reasons may be allowed if approved by the BMS medical monitor.

Prior to re-initiating treatment in a subject with a dosing delay lasting > 6 weeks, the BMS medical monitor must be consulted. Tumor assessments should continue as per protocol even if dosing is delayed. Periodic study visits to assess safety and laboratory studies should also continue every 6 weeks or more frequently if clinically indicated during such dosing delays.

- Any adverse event, laboratory abnormality, or intercurrent illness which, in the judgment of the Investigator, presents a substantial clinical risk to the subject with continued nivolumab dosing.

Tumor assessments for all subjects should continue as per protocol even if study drug dosing is interrupted.

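### Protocol 4.5.3.1's Grade 4 endocrinopathy exception omits the adrenal-insufficiency carve-out found in 4.5.2.1 and in its own Grade 3 bullet, so the stopping rule for controlled Grade 4 adrenal insufficiency is not settled

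*Protocol*

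**What the plan says.** Three statements in the Protocol bear on adrenal insufficiency in Arm A.

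- **Section 4.5.2.1, Criteria to Resume Treatment.** The general allowance is "Subjects with drug-related endocrinopathies adequately controlled with only physiologic hormone replacement may resume treatment after consultation with the BMS Medical Monitor". The next sentence takes adrenal insufficiency out of it, requiring discontinuation whatever the hormone control. No grade is given.
- **Section 4.5.3.1, Grade 3 endocrinopathy sub-bullet.** The allowance is "Grade 3 drug-related endocrinopathies adequately controlled with only physiologic hormone replacement do not require discontinuation". After a semicolon comes the same carve-out: "Adrenal insufficiency requires discontinuation regardless of control with hormone replacement". The sentence names no grade itself but sits among the Grade 3 exceptions.
- **Section 4.5.3.1, Grade 4 bullet.** Any Grade 4 drug-related event leads to permanent discontinuation, "except for the following events which do not require discontinuation". One listed exception is "Grade 4 drug-related endocrinopathy adverse events, such as hyper- or hypothyroidism, or glucose intolerance", if these are events "which resolve or are adequately controlled with physiologic hormone replacement (corticosteroids, thyroid hormones) or glucose-controlling agents". Such events "may not require discontinuation after discussion with and approval from the BMS Medical Monitor". There is no adrenal carve-out here.

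**The concern.** For adrenal insufficiency, the first two statements make hormone control irrelevant. The Grade 4 exception makes hormone control, expressly including control with corticosteroids, the ground on which treatment may go on. The carve-out is attached to two of the three endocrinopathy allowances and missing from the third. The text does not show whether the omission is deliberate.

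The rule at issue is a permanent-stopping rule for a Grade 4 event in an open-label, multinational trial. If two sections give different answers, identical events can be managed differently across sites. A continuation properly approved under 4.5.3.1 could also breach 4.5.2.1.

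**Working it through.** No sample size, event count, power or alpha enters this point, so the check is a comparison of texts.

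| Statement | Grade stated | Adrenal insufficiency | Effect if controlled on replacement |
|---|---|---|---|
| 4.5.2.1, resume criteria | None | Named | Discontinue |
| 4.5.3.1, Grade 3 sub-bullet | None in the sentence; placed under Grade 3 | Named | Discontinue |
| 4.5.3.1, Grade 4 exception | Grade 4 | Neither named nor excluded | May continue with Medical Monitor approval, if the event falls within the exception |

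Take one test case: drug-related Grade 4 adrenal insufficiency, adequately controlled on physiologic corticosteroid replacement, with continuation approved by the Medical Monitor.

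1. **General Grade 4 rule (4.5.3.1).** Nivolumab stops unless an exception applies.
2. **Does the Grade 4 exception reach it?** The class is drug-related endocrinopathy. Thyroid events and glucose intolerance are introduced by *such as*, so they are examples and not a closed list. The control criterion counts corticosteroids as physiologic hormone replacement. The Protocol uses steroid replacement in the adrenal sense elsewhere, in exclusion criterion 2d (3.3.2) and in Permitted Therapy (3.4.3). Nothing excludes adrenal events. The case fits the wording and may continue.
3. **Resume criteria (4.5.2.1).** Adrenal insufficiency is named, with no grade limit. The case must discontinue.
4. **Adrenal sentence in the Grade 3 sub-bullet (4.5.3.1).** If its placement confines it to Grade 3, it is silent on this case, and the conflict is between steps 2 and 3. If it covers all grades, it conflicts with step 2 inside the same section.
5. **Precedence.** No sentence in 4.5.2.1 or 4.5.3.1 says which statement governs.

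Steps 2 and 3 therefore give different answers for the same event, and either reading of step 4 leaves the conflict in place.

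**The case against.** The best defence is that the conflict is softer than the table suggests.

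- **The adrenal sentence carries no grade in either place.** Both can be read as covering all grades, and a sentence that names a condition is naturally read over a general exception that does not. If nivolumab is withheld, re-dosing also passes through 4.5.2.1, where adrenal insufficiency is barred. This is a sensible reading, but no text adopts it. Section 4.5.3.1 is the dedicated discontinuation section, and its Grade 4 exception is the more grade-specific text. Even if 4.5.2.1 governs, the Grade 4 bullet invites an approval request for something another section forbids.
- **Adrenal insufficiency enters the Grade 4 exception only by inference**, through *such as* and the mention of corticosteroids. The closing *respectively* can be taken to pair the named events with their treatments, which favours a narrower reading. It does not close the list.
- **The exception is not automatic.** It is permissive and needs Medical Monitor discussion and approval. Section 4.5.3.1 separately requires discontinuation for any event that the investigator judges a substantial clinical risk. These are real safeguards, but they do not tell the Medical Monitor which statement to apply.
- **Other material may settle it.** The Appendix 1 endocrinopathy algorithm is a figure not shown, and 4.5.1.1 also points to the Investigator Brochure. Neither could be checked.

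A reader might go further and infer that the Protocol plainly stops Grade 3 adrenal insufficiency while letting Grade 4 continue. The documents do not support that. It requires confining the 4.5.3.1 adrenal sentence to Grade 3, setting 4.5.2.1 aside, and overlooking the approval condition.

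**Conclusion.** The text is wrong as written. It is an internal inconsistency in a permanent-stopping rule, not a design choice. The Grade 4 exception can be read to allow continued nivolumab after an event for which two other statements require discontinuation, and nothing ranks them.

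The scope is narrow. A reader might take every Grade 4 adrenal insufficiency event in Arm A to be affected, but only drug-related events that resolve or are adequately controlled come within the exception, and continuation also needs approval. All others stop under the general Grade 4 rule. The documents give no rate. The endocrine select events itemised for CA209037 in 1.1.3.3 are hypothyroidism and hyperthyroidism, so there is no figure to scale from; a small number is an assumption. No consequence for an endpoint, the sample size or an analysis is shown. What is at stake is patient safety and uniform handling across sites.

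The conclusion rests on reading *such as* as an open list and corticosteroids as including adrenal replacement, and on the visible text alone. It takes no view on which clinical rule is right.

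**What to change.** Reconcile the Grade 4 endocrinopathy exception in 4.5.3.1 with the adrenal-insufficiency statements in 4.5.2.1 and in the Grade 3 sub-bullet of 4.5.3.1. The rule for each grade should be explicit and read the same in both sections. The clinical team decides which rule applies. At the same time, check the endocrinopathy algorithm in Appendix 1 and the Investigator Brochure against the reconciled text.

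The cost is about one clause in the Protocol, carried in an amendment. The SAP analyses do not need to change.
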